6.3 Lifestyle Restrictions

Based on the number of PK sampling timepoints, an overnight stay in the clinic is recommended for the Day 1 (Mini Age Cohort 1 only) and Week 4 visits (all participants).

6.3.1 Meals and Dietary Restrictions

EBR/GZR (FDC) can be taken without regard to food; however, intake of EBR/GZR pediatric formulation must be mixed in a soft food dosing vehicle (applesauce, pudding, or yogurt).

6.4 Screen Failures

Screen failures are defined as participants who consent/assent to participate in the clinical study but are not subsequently entered in the study. A minimal set of screen failure information is required to ensure transparent reporting of screen failure participants to meet the Consolidated Standards of Reporting Trials (CONSORT) publishing requirements and to respond to queries from regulatory authorities. Minimal information includes demography, screen failure details, eligibility criteria, and any adverse events or serious adverse events (SAE) meeting reporting requirements as outlined in the entry guidelines.

6.5 Participant Replacement Strategy

If a participant discontinues from trial treatment prior to intensive PK sampling at TW4, a replacement participant may be enrolled if deemed appropriate by the Sponsor. The replacement participant will be matched to the same cohort and receive the same treatment as the participant being replaced. The replacement participant will be assigned a unique treatment/allocation number. The trial site should contact the Sponsor for the replacement participant's treatment/allocation number.

7. Treatments

Study treatment is defined as any investigational treatment(s), marketed product(s), placebo, or medical device(s) intended to be administered to a study participant according to the study protocol.

Clinical supplies [study treatment(s) provided by the Sponsor] will be packaged to support enrollment as required. Clinical supplies will be affixed with a clinical label in accordance with regulatory requirements.

7.1 Treatments Administered

The study treatments to be used in this trial are outlined below in [Table 5](#).

Table 5 Study Treatments

Study Treatment Name:	EBR/GZR FDC	Placebo to match MK-5172A (EBR/GZR) FDC*	MK-8742 (EBR) Pediatric Formulation	MK-5172 (GZR) Pediatric Formulation
Dosage Formulation:	Tablet	Tablet	Oral granules***	Oral granules***
Unit Dose Strength(s):	50 mg/100 mg	0 mg/0 mg	0.5 mg	1 mg
Dosage Level(s):	1 tablet QD	1 tablet given prior to allocation**	TBD – dose will not exceed 50 mg	TBD – dose will not exceed 100 mg
Route of Administration:	Oral	Oral	Oral	Oral
Sourcing:	Sponsor	Sponsor	Sponsor	Sponsor

*Placebo tablets are different in color but identical in size and shape to the active EBR/GZR FDC tablets.

**Placebo to EBR/GZR (FDC) tablet is given once prior to allocation to participants in Mini Age Cohort 1. This will also apply to participants in Expanded Age Cohort 1 if it is determined by PK analysis that Expanded Age Cohort 1 will also receive the adult FDC dose.

***Pediatric formulation supplied as single entity packets.

EBR = elbasvir; FDC = fixed dose combination; GZR = grazoprevir; PK = pharmacokinetics; QD = once-daily; TBD = to be determined.

As PK data becomes available, the dose proposed for participants will be adjusted to meet the scientific goals and study objectives.

Mini Age Cohort 1 will be administered FDC tablets (EBR 50 mg/GZR 100 mg). Expanded Age Cohort 1 is expected to receive FDC tablets but alternatively may receive pediatric formulation, if PK data suggests a lower dose (dosage to be informed by trial). Age Cohorts 2 and 3 will be administered pediatric formulation product (dosage to be informed by trial). Following assignment of formulation, participants may not change from FDC tablets to pediatric formulation or from pediatric formulation to FDC tablets during the course of the trial.

The pediatric formulation in this study allows for flexibility of dosing. EBR 0.5 mg and GZR 1.0 mg are packaged as single entity packets, which contain oral granules. The foil packets are opened and the contents (oral granules) are mixed into a soft food vehicle (applesauce, pudding, or yogurt) prior to consumption.

Each single entity packet is individually labeled with the Sponsor's product number (MK-8742 is EBR; MK-5172 is GZR) and contains 10 oral granules of either EBR or GZR.

- EBR packets have 5 mg per unit package and
- GZR packets have 10 mg per unit package

The recommended dosing for each Age Cohort will be detailed by the Sponsor in a memo to the Study File. Dosing recommendations for Mini Age Cohort 3 and all Expanded Age Cohort(s) will be by weight bands, which will be determined based on PK analyses. This memo will be communicated to the site personnel. The memo should be forwarded to the Institutional Review Board/Ethics Review Committee (IRB/ERC) by the Investigator, as appropriate per IRB/ERC guidelines.

All placebos were created by the Sponsor to match the active product.

All supplies indicated in [Table 5](#) will be provided per the ‘Sourcing’ row depending upon local country operational requirements. Every attempt should be made to source these supplies from a single lot/batch number. The trial site is responsible for recording the lot number, manufacturer, and expiry date for any locally purchased product as per local guidelines unless otherwise instructed by the Sponsor.

Refer to section 9.1.8 for details regarding administration of the study treatment.

7.2 Dose Modification (Escalation/Titration/Other)

Dose modification of EBR/GZR is not permitted by the site personnel. For more information on dose modification during the course of the trial, see Section 5.5.1.1.

7.3 Method of Treatment Assignment

Participants will be allocated to treatment via an interactive voice response system/interactive web response system (IVRS/IWRS) by non-random assignment.

7.3.1 Stratification

Treatment allocation/randomization will be stratified according to the following factors:

By design, participants will be stratified by Age Cohorts (3 years to <7 years, 7 years to <12 years, 12 years to <18 years).

7.4 Blinding

This is an open-label trial; therefore, the Sponsor, investigator and participant will know the treatment administered.

7.5 Preparation/Handling/Storage/Accountability

7.5.1 Dose Preparation

The study is designed with staged enrollment. PK data from earlier enrolled cohorts within the study will inform the recommended daily dose of EBR and GZR for subsequently enrolled cohorts. Details are provided in Section 5.5 – Justification for Dose.

Once the Sponsor has determined and communicated recommended dosing for subsequent cohorts receiving the pediatric formulation of EBR/GZR, site personnel will count and package the appropriate number of EBR and GZR single entity packets for each participant’s daily dose. Daily dosage preparation will be multiples of individually labeled unopened packets.

7.5.2 Handling, Storage and Accountability

The investigator or designee must confirm appropriate temperature conditions have been maintained during transit for all study treatment received and any discrepancies are reported and resolved before use of the study treatment.

Only participants enrolled in the study may receive study treatment and only authorized site staff may supply or administer study treatment. All study treatments must be stored in a secure, environmentally controlled, and monitored (manual or automated) area in accordance with the labeled storage conditions with access limited to the investigator and authorized site staff.

The investigator, institution, or the head of the medical institution (where applicable) is responsible for study treatment accountability, reconciliation, and record maintenance (ie, receipt, reconciliation, and final disposition records).

For all trial sites, the local country Sponsor personnel or designee will provide appropriate documentation that must be completed for drug accountability and return, or local discard and destruction if appropriate. Where local discard and destruction is appropriate, the investigator is responsible for ensuring that a local discard/destruction procedure is documented.

The trial site is responsible for recording the lot number, manufacturer, and expiry date for any locally purchased product as per local guidelines unless otherwise instructed by the Sponsor.

The investigator shall take responsibility for and shall take all steps to maintain appropriate records and ensure appropriate supply, storage, handling, distribution and usage of study treatments in accordance with the protocol and any applicable laws and regulations.

7.6 Treatment Compliance

The participant/legally acceptable representative will be provided a Study Medication and Meal Diary (SMD) to record the number of FDC tablets or EBR/GZR pediatric formulation packets taken during the treatment period (Section 9.11.2). At all visits during the treatment period, site personnel must verify the accuracy of the dosing SMD by comparing entries with amounts of unused study medication. If a discrepancy is noted, investigator/study coordinator must discuss the discrepancy with the participant/legally acceptable representative and the explanation must be documented.

Administration of trial medication will be witnessed by the investigator and/or trial staff at the Day 1, TW4, and TW8 (visits where the predose PK samples will be collected).

Missed Doses

If a participant misses a dose (or any part thereof) of EBR/GZR, the next dose should not be doubled in order to compensate for what has been missed. The participant should be instructed as follows:

- If the next dose is in more than 8 hours, the missed dose should be taken as soon as possible and the normal dosing schedule resumed.

- If the next dose is less than 8 hours, the missed dose should be skipped and the normal dosing schedule resumed.

Treatment Interruptions

Treatment interruptions should be avoided, but if for any reason EBR/GZR needs to be interrupted, it can be interrupted for up to 3 consecutive days.

Interruptions from the protocol specified treatment for >3 consecutive days require consultation between the investigator and the Sponsor and written documentation of the collaborative decision on participant management.

7.7 Concomitant Therapy

Medications or vaccinations specifically prohibited in the exclusion criteria are not allowed during the dosing period. If there is a clinical indication for any medication or vaccination specifically prohibited, discontinuation from trial therapy or vaccination may be required. The investigator should discuss any questions regarding this with the Sponsor Clinical Director. The final decision on any supportive therapy or vaccination rests with the investigator and/or the participant's primary physician. However, the decision to continue the participant on study treatment requires the mutual agreement of the investigator, the Sponsor and the participant or the participant's legally acceptable representative.

It is important for investigators to review each medication (prescription and non-prescription) the participant is taking before starting the study and at each study visit.

- All concomitant medications should be reviewed and data collected through 2 weeks after the study treatment period. Participants or the participant's legally acceptable representative should be asked about any new drugs/vaccines they are taking/have taken or changes to any previously reported drugs/vaccines.
 - Drugs known to be hepatotoxic (ie, drugs with a warning of hepatotoxicity in the package insert) should be avoided. Investigators are encouraged to review each medication for potential hepatotoxicity using the website www.livertox.nih.gov.
- To minimize the risk of adverse drug interactions, every effort should be made to limit the number of concomitant drugs to those that are truly essential.
- Non-study HCV medications/therapies, including IFN, are prohibited through FW24. Any use should be reported throughout the study duration.

Prohibited Medication

Specific restrictions for concomitant therapy are listed in [Table 6](#). The medications/therapies are not permitted during the dosing period and for 14 days thereafter.

Table 6 List of Prohibited Medications

Known hepatotoxic drugs	Etifoxine, isoniazid, nitrofurantoin, phenytoin, oral ketoconazole
Herbal supplements	Including, but not limited to: St. John's wort
Strong and moderate CYP3A/P-gp inducers, including but not limited to	Anti-infectives: nafcillin, rifampin Anticonvulsants: carbamazepine, phenytoin, phenobarbital Endothelin antagonists: bosentan Wakefulness-promoting agents: modafinil Herbal products: St. John's wort HIV medications: efavirenz, etravirine
OATP inhibitors	Immunosuppressants: cyclosporine Anti-infectives: rifampin HIV medications: atazanavir, darunavir, lopinavir, saquinavir, tipranavir
HCV medications	All non-study HCV medications/therapies
HIV medications, including but not limited to	All boosted and unboosted HIV protease inhibitors including, but not limited to: atazanavir, darunavir, lopinavir, saquinavir, tipranavir Cobicistat-containing regimens: elvitegravir/cobicistat/emtricitabine/tenofovir (disoproxil fumarate or alafenamide) efavirenz etravirine
HMG-CoA reductase inhibitors (statins)	All statins are prohibited during the dosing period of the study
Investigational agents	All investigational agents (aside from study-related therapies)
Systemic corticosteroids	Systemic corticosteroid use for more than 2 weeks (except pulmonary/nasal administration)

AE=adverse event; CYP3A/P-gp=cytochrome P4503A/P-glycoprotein; HCV=hepatitis C virus; HIV=human immunodeficiency virus; HMG-CoA=3-hydroxy-3-methylglutaryl-coenzyme A; OATP=organic anion-transporting polypeptide.

In addition to the medications listed in [Table 6](#), participants in the Mini Age Cohorts are prohibited from taking the following medications:

- Strong CYP3A inhibitors: Including but not limited to, clarithromycin, telithromycin, itraconazole, ketoconazole, nefazodone
- Methadone

Allowed Medications

Table 7 List of Allowed Medications

Commonly Used for the Pediatric Population	
Hypoglycemic agents	Insulin, sitagliptin, glipizide, metformin
Contraceptives	Oral contraceptive pills, progesterone injects, intrauterine devices
Antidepressants/anxiolytics	Citalopram, paroxetine, duloxetine, escitalopram, fluoxetine, bupropion, trazodone, diazepam, clonazepam, temazepam, lorazepam
Acid reflux	Acid blockers: H ₂ blockers and proton pump inhibitors
Asthma	histamine blockers, inhaled/nasal corticosteroids, montelukast
Less Commonly Used for the Pediatric Population	
Anti-coagulants	Warfarin, heparin, low molecular weight heparin, aspirin, fondaparinux, desirudin, acenocoumarol
Antihypertensives	Angiotensin-converting enzyme inhibitors or angiotensin receptor blockers: enalapril, captopril, lisinopril, ramipril, valsartan, losartan, telmisartan Beta blockers: atenolol, metoprolol, propranolol (for other beta blockers, please consult with the Sponsor) Calcium-channel blockers: amlodipine, diltiazem, verapamil (for other calcium-channel blockers, please consult with the Sponsor) Hydralazine, clonidine, minoxidil, isosorbide nitrates
Anemia	Erythropoietin
Diuretics	Hydrochlorothiazide, furosemide, spironolactone, triamterene
Opiate substitution therapy	Buprenorphine/naloxone, methadone Note: Participants in the Mini Age Cohorts are prohibited from taking methadone
Immunosuppressants	Prednisone, daily doses <10 mg or a short course lasting <2 weeks for higher doses.

Given that the lists above are not comprehensive, the investigator should use his/her medical judgment when a participant presents with a medication not on the list and consult with the Sponsor.

Concomitant medications and therapies discontinued during the dosing period may be restarted 2 weeks after the last dose of study drug is administered and may continue during the follow-up period.

7.7.1 Rescue Medications & Supportive Care

No rescue or supportive medications are specified to be used in this trial.

7.8 Treatment After the End of the Study

There is no study-specified treatment following the end of the study.

7.9 Clinical Supplies Disclosure

This trial is open-label; therefore, the participant/legally acceptable representative, the trial site personnel, the Sponsor and/or designee are not blinded. Study treatment (name, strength or potency) is included in the label text; random code/disclosure envelopes or lists are not provided.

8. Discontinuation/Withdrawal Criteria

8.1 Discontinuation of Study Treatment

Discontinuation of study treatment does not represent withdrawal from the study.

As certain data on clinical events beyond study treatment discontinuation may be important to the study, they must be collected through the participant's last scheduled follow-up, even if the participant has discontinued study treatment. Therefore, all participants who discontinue study treatment prior to completion of the protocol-specified treatment period will still continue to participate in the study as specified in Section 2 - SoA and Section 9.11.4 – Discontinued Participants Continuing to be Monitored in the Study.

Participants may discontinue study treatment at any time for any reason or be dropped from the study treatment at the discretion of the investigator should any untoward effect occur. In addition, a participant may be discontinued from study treatment by the investigator or the Sponsor if study treatment is inappropriate, the trial plan is violated, or for administrative and/or other safety reasons. Specific details regarding procedures to be performed at study treatment discontinuation are provided in Section 9.1.9 – Withdrawal/Discontinuation.

A participant must be discontinued from study treatment but continue to be monitored in the study for any of the following reasons:

- The participant or participant's legally acceptable representative requests to discontinue study treatment.
- The participant has a medical condition or personal circumstance which, in the opinion of the investigator and/or sponsor, placed the participant at unnecessary risk from continued administration of study treatment.
- Participant meets any HCV virologic failure criteria (see Section 5.4.2.1.1).
- The participant has a confirmed positive serum pregnancy test.
- A physician feels it is in the best interest of the participant to discontinue.
- ALT or AST increases to >500 IU/L and is confirmed with repeat test immediately.
- ALT or AST increases to $>3\times$ baseline and/or nadir, is >100 IU/L, and there is a simultaneous increase in total bilirubin $>2\times$ ULN and/or INR is increased from the baseline value and is >1.5 (unless the participant is on anticoagulation).
- Alkaline phosphatase increases to $>3\times$ ULN, there is a simultaneous increase in total bilirubin $>2\times$ ULN, and other causes of elevated alkaline phosphatase are excluded.

- Alkaline phosphatase increases to $>5 \times$ ULN and other causes of elevated alkaline phosphatase are excluded.
- The participant has a life-threatening clinical or laboratory AE or an event that results in or prolongs an existing inpatient hospitalization that is assessed to be a study drug-related laboratory or clinical AE.

A participant **may** be discontinued from treatment but continue to be monitored in the study for any of the following reasons:

- SAE assessed by the physician investigator as possibly or probably related to study medication. Investigator may continue the participant in the trial, if it is deemed to be in the best interest of the participant to stay on the study treatment.
- Failure to comply with the dosing, evaluations, or other requirements of the trial.

For participants who are discontinued from study treatment but continue to be monitored in the trial, all visits and procedures, as outlined in the SoA, should be completed.

Participants may be allowed to begin study treatment again if deemed medically appropriate, upon consultation with the Sponsor.

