9.3.4 Regulatory Reporting Requirements for SAE

- Prompt notification (within 24 hours) by the investigator to the sponsor of SAE is essential so that legal obligations and ethical responsibilities towards the safety of participants and the safety of a study treatment under clinical investigation are met.
- The sponsor has a legal responsibility to notify both the local regulatory authority and other regulatory agencies about the safety of a study treatment under clinical investigation. All Adverse Events will be reported to regulatory authorities, IRB/IECs and investigators in accordance with all applicable global laws and regulations, ie, per ICH Topic E6 (R1) Guidelines for Good Clinical Practice.
- Investigator safety reports must be prepared for suspected unexpected serious adverse reactions (SUSAR) according to local regulatory requirements and sponsor policy and forwarded to investigators as necessary.
- An investigator who receives an investigator safety report describing a SAE or other specific safety information (eg, summary or listing of SAE) from the sponsor will file it along with the Investigator's Brochure and will notify the IRB/IEC, if appropriate according to local requirements.

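### Section 8.1 makes stopping mandatory for drug-related life-threatening or hospitalization events, but its optional SAE bullet also covers them and lets treatment continue

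*Combined protocol and SAP*

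**What the plan says.** Section 8.1 opens its binding list with "A participant must be discontinued from study treatment but continue to be monitored in the study for any of the following reasons". The last of its ten bullets reads in part "The participant has a life-threatening clinical or laboratory AE or an event that results in or prolongs an existing inpatient hospitalization", and requires that the event be assessed as study drug-related.

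A second list follows, of reasons for which a participant may be discontinued. Its first bullet is "SAE assessed by the physician investigator as possibly or probably related to study medication". The sentence after it allows the investigator to continue the participant "if it is deemed to be in the best interest of the participant to stay on the study treatment".

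After both lists comes a restart provision: "Participants may be allowed to begin study treatment again if deemed medically appropriate, upon consultation with the Sponsor".

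Appendix 4 defines an SAE by six criteria, (a) to (f). Criterion (b) is a life-threatening event. Criterion (c) is inpatient hospitalization or its prolongation.

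**The concern.** A permissive rule that overlaps a mandatory one usually does no harm: a participant who must stop is also one who may stop. Here the permissive bullet goes further. Its second sentence gives the investigator a stated ground for keeping the participant on treatment, and neither the bullet nor that sentence excludes events already on the mandatory list.

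The trial treats children aged 3 to under 18 years, and the rule decides whether exposure continues after a serious drug-related event. Two sites facing the same event could each point to a line in Section 8.1 and act differently. Whether that participant then counts toward the secondary endpoint on discontinuations due to AEs (Section 4) could also depend on which line the site followed.

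**Working it through.** There is no figure to reproduce. The check is a comparison of the two Section 8.1 lists with the SAE definition and causality scale in Appendix 4.

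**Step 1: which drug-related SAEs fall under each bullet**

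| Appendix 4 SAE criterion | Mandatory last bullet | Optional SAE bullet |
|---|---|---|
| (a) death | moot | moot |
| (b) life-threatening | yes | yes |
| (c) hospitalization or prolongation | yes | yes |
| (d) disability | no | yes |
| (e) congenital anomaly | no | yes |
| (f) other important medical event | no | yes |

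The overlap is rows (b) and (c), two of six categories. Rows (d) to (f) belong to the optional bullet alone, unless the event also meets (b), (c) or another mandatory criterion. Limiting the optional bullet to other SAEs would therefore still leave it with content.

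**Step 2: does causality wording separate the bullets?** The mandatory bullet asks for a study drug-related assessment; the optional one asks for possibly or probably related. Appendix 4 records only Yes or No. Its Yes category describes an event more likely explained by the product than by another cause, and a probably related SAE fits that naturally, so the overlap exists at least there. A possibly related SAE is less clear: the documents do not map it to Yes, and it might be recorded as No. The optional bullet may therefore also reach weaker-causality events that the mandatory bullet does not.

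**Step 3: does any text rank the lists?** The optional bullet does not say it is confined to other SAEs, it contains no exclusion, and no precedence rule appears elsewhere.

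**Step 4: does the restart provision reconcile them?** No. It applies after a stop and requires Sponsor consultation. The optional bullet allows continuation without a stop, on the investigator's judgment.

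**Step 5: what depends on the answer?** The pause rule in Section 5.4.2.3.2 counts participants who have the event, whether or not they stop treatment. PK endpoints and sample size do not use Section 8.1 status for such events. Section 10.3 states that the trial tests no hypotheses.

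**The case against.** The strongest reply is that the mandatory wording plainly governs. That bullet is specific, comes first, and sits under an unqualified requirement. The optional sentence does not claim to override it, and saying that a participant may be discontinued already implies that the participant need not be. On this reading the optional bullet serves the remaining related SAEs, every word has effect, and a site goes wrong only by disregarding an explicit requirement. This is the better reading, and the fix below adopts it. It does not dispose of the point, because the reader must supply the ranking, and a stopping rule should not need interpretation when a child has just been hospitalized.

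The reply that safeguards exist also stands in part. Section 9.3.4 says "Prompt notification (within 24 hours) by the investigator to the sponsor of SAE is essential". Under Section 8.1 "a participant may be discontinued from study treatment by the investigator or the Sponsor if study treatment is inappropriate", and the mandatory list separately covers a condition that, "in the opinion of the investigator and/or sponsor, placed the participant at unnecessary risk from continued administration of study treatment". A site that wrongly continued treatment would therefore be visible to the Sponsor quickly and could be corrected. These provisions limit the harm but leave the two instructions unreconciled.

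A reader might infer that Section 8.1 expressly permits continued dosing after a must-stop event. It does not. The permission to continue is express, but the optional bullet never names life-threatening or hospitalization events and reaches them only through the term SAE.

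**Conclusion.** Wrong as written: two stated rules give contrary instructions for the same event. Severity is low. The conflict touches one of ten mandatory criteria, and its effect is limited to whether sites apply a safety stopping rule consistently.

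The conclusion rests on two readings: that SAE in the optional bullet carries its Appendix 4 meaning, and that at least a probably related event counts as study drug-related under the mandatory bullet. Both follow the ordinary sense of the text.

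Two further inferences are not supported. A reader might think the safety results are materially at risk, since one discontinuation changes a percentage noticeably in a small cohort. That would be true of any single event; the documents give no rate for these events, and the endpoint is descriptive, so no numerical size is claimed. A reader might also conclude that Section 8.1 should move to the Yes/No causality scale. Because possibly related is not mapped to Yes, that change could remove some SAEs from the optional list.

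**What to change.** Leave the mandatory bullet as it stands. Reword the optional bullet so that it begins with Other SAE, adds the qualifier that the event does not meet any mandatory discontinuation criterion above, and keeps its present causality wording. State that the best-interest sentence applies only to those events. Referring to any mandatory criterion also settles the case of a related SAE that meets one of the hepatic thresholds.

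The restart provision and the Appendix 4 rechallenge note already set out Sponsor involvement before re-exposure and need no change for this point.

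The cost is one reworded bullet in an amendment, with no new data, visits or staff.
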